7.4.2 SERIOUS ADVERSE EVENT REPORTING PROCESS

SAEs and unanticipated events, which are considered “at least possibly related” during the treatment and follow-up phases, must be reported to the local IRB and to the NIAAA project officer within 48 hours of knowledge of the SAE. All other SAEs and unanticipated events must be reported within the time period mandated by the local IRB.

Clinical sites will follow local reporting procedures for reporting SAEs to their IRB/EC. Where required by local legislation any SAE occurring within 30 days after the last clinical site visit will also be documented, collected and reported if appropriate. However, clinical site assessors do not need to actively monitor a participant for new SAEs after the final clinical site visit.

7.4.3 ADVERSE EVENTS OF SPECIAL INTEREST IN MACH15 (SAE AND MACH15 AE)

There is special interest in a number of AEs or SAEs due to their relationship to alcohol consumption.³ Participants will be queried about these MACH15 events specifically at their regular contacts and visits. Please note that a MACH15 AE can also be a SAE. The MACH15 AEs include:

- Total and site-specific cancer excluding non-melanoma types of skin cancer
- Road or water accidents that require medical attention
- Major falls requiring medical attention in the hospital or emergency ward
- Fall-related fractures (i.e., only fractures resulting from a fall, not due to disease, illness or non-fall-related fractures)
- Atrial fibrillation requiring hospitalization
- Congestive heart failure (CHF) requiring hospitalization
- Hemorrhagic stroke requiring hospitalization

In addition, investigators will report the following:

- Increase in liver tests to >2 times the upper limit of normal (ULN)
- Alcohol use disorder

- Unexpected events for which the clinician believes that participation in MACH15 caused the event or contributed to the immediate cause of the event

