3.5.2 OUTCOMES DEFINITIONS

Myocardial Infarction (MI): Defined as the death of part of the myocardium due to an occlusion of a coronary artery from any cause, including spasm, embolus, thrombus or rupture of a plaque. MACH15 will use standard case definitions for both fatal and nonfatal MI based on the combination of symptoms, elevation in biomarkers, and/or ECG findings. The algorithm for classifying MI includes elements of the clinical presentation (signs and symptoms), results of cardiac biomarker determinations, and ECG readings, and is based on the 2003 American Heart Association Position Statement “Case Definitions for Acute Coronary Heart Disease in Epidemiology and Clinical Research Studies”² and consideration of the 2012 “Third Universal Definition of Myocardial Infarction”.³ MACH15 adjudicators will be guided by specific, pre-specified definitions and operational rules. Adjudicators will use their clinical interpretation of the ECGs and other available evidence for the event to classify the MI.²

Stroke: MACH15 will use standard case definitions for both fatal and nonfatal stroke. Stroke will be defined based on all available data, including symptoms and signs, imaging of the brain and large vessels, and cardiac testing, e.g., echocardiography. Based on “An Updated Definition of Stroke for the 21st Century” AHA/ASA Expert Consensus Document,⁴ central nervous system (CNS) infarction will be defined as A) pathological, imaging, or other objective evidence of CNS injury in a defined vascular distribution; or B) clinical evidence of CNS injury based on symptoms persisting ≥ 24 hours or until death, and other etiologies excluded. Exclusionary conditions for stroke include major brain trauma, intracranial neoplasm, coma due to metabolic disorders or disorders of fluid or electrolyte balance, peripheral neuropathy, or central nervous system infections. In cases where there is enough documentation, stroke will be classified by subtype.

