7.1.2 DEFINITION OF SERIOUS ADVERSE EVENTS (SAE)

The OHRP defines Serious Adverse Events (SAE) as any AE that:

- results in death;
- is life-threatening (places the participant at immediate risk of death from the event as it occurred);
- results in inpatient hospitalization or prolongation of existing hospitalization;
- results in a persistent or significant disability/incapacity;
- results in a congenital anomaly/birth defect; or
- based upon appropriate medical judgment, may jeopardize the participant's health and may require medical or surgical intervention to prevent one of the other outcomes listed in this definition.

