7.3 TIME PERIOD AND FREQUENCY FOR EVENT ASSESSMENT AND FOLLOW-UP

The documentation and collection of all SAEs and all MACH15 AEs will begin after Informed Consent is obtained and end after procedures for the final visit have been completed. Participants will be contacted and interviewed regarding possible SAEs and MACH15 AEs in a standardized fashion throughout the trial according to the Visit Schedule (Table 6.1: Measures and Frequency Table). If a participant has died or cannot be reached, their alternate contact will be interviewed if allowed by local legislation. SAEs and MACH15 AEs (Section 7.4) will be investigated through the collection of data during this interview process, the abstraction or acquisition of copies of medical records, emergency medical services reports, death certificates, coroner and/or autopsy reports, and/or the completion of attending physician questionnaires, as appropriate. In addition to fixed time points, events may be received spontaneously via the participant, proxy, or a member of the clinical site staff. All clinical sites will take appropriate action regarding the event and will be responsible for documenting, collecting, processing, classifying, and coding MACH15 AEs and SAEs within the online safety collection system within the secure MACH15 website.

The clinical site Principal Investigator (PI) will submit all safety updates and periodic reports to the Regulatory Authority(ies) and local IRB/EC, as required by applicable local regulatory requirement(s). Individual safety reports, if required, will be created by the clinical site PI. Central, trial-wide SAE listings and an annual safety report will be provided to the DSMB.

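### The named alcohol-related AE categories for hemorrhagic stroke, heart failure and major falls have no fatal-event clause, so out-of-hospital deaths from these harms are captured as SAEs and deaths but not clearly in the by-arm count of each harm

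*Combined protocol and SAP*

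**What the plan says.** Section 7.4.3 names the adverse events singled out for their link to alcohol. Four of its items matter here:

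- "Hemorrhagic stroke requiring hospitalization"
- "Congestive heart failure (CHF) requiring hospitalization"
- "Major falls requiring medical attention in the hospital or emergency ward"
- "Road or water accidents that require medical attention"

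Atrial fibrillation also carries a hospitalization condition. Cancer and fall-related fractures do not; the fracture item begins "Fall-related fractures (i.e., only fractures resulting from a fall" and sets no care threshold.

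Other sections bear on how a death is recorded. Under 7.1.2 an adverse event that "results in death" is serious whatever the setting. Section 7.4 has all SAEs reported centrally, and 7.3 sends trial-wide SAE listings to the DSMB. For investigating events, 7.3 provides for interviews with an alternate contact where local law allows, ambulance-service records, and "death certificates, coroner and/or autopsy reports". All-cause mortality is part of the primary endpoint and a tertiary outcome in its own right (3.5.1), and 7.1 has trial outcomes monitored as safety events too.

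On stroke, 3.5.2 states: "MACH15 will use standard case definitions for both fatal and nonfatal stroke", with subtype assigned where documentation is sufficient. The same section ties cardiovascular death to infarction, ischemic stroke, admission for angina, and coronary or carotid revascularization.

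Section 8.1.3 gives the safety events that the DSMB will monitor. It names falls, atrial fibrillation and hemorrhagic stroke with no care condition, names motor vehicle collisions where 7.4.3 has road or water accidents, and does not name heart failure.

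**The concern.** The protocol's own background (1.2.2) reports that hemorrhagic stroke rises with alcohol dose, and 1.2.4 says that trauma may rise even with moderate drinking. Section 8.1.3 makes consideration of stopping for safety depend on how event rates in the alcohol arm compare with those in the abstention arm. Those rates need a definition that includes the worst form of each harm. As 7.4.3 is worded, a participant admitted with a hemorrhagic stroke who survives is an event for that category, while one who dies of it at home may not be.

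Case-by-case review of SAEs is a weak substitute. Section 7.2.2 anticipates that cardio-metabolic events and accidents will often be classed as expected in this population, so a single report is unlikely to stand out. All-cause mortality is a weak substitute too, because it pools these deaths with those that the trial hypothesizes alcohol will prevent. A difference between arms in one of these harms would show most directly in its own by-arm count.

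**Working it through.** The point concerns definitions, and the plan gives no figure to reproduce. The check is to follow a death without hospital contact through each route by which the protocol could record it.

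| Fatal event, no hospital contact | SAE (7.1.2) | All-cause death (3.5.1) | Cardiovascular death by cause (3.5.2) | Named item in 7.4.3, literal reading | Named in 8.1.3 |
|---|---|---|---|---|---|
| Hemorrhagic stroke | Yes | Yes | No | No | Yes, no care condition |
| Heart failure | Yes | Yes | No | No | Not named |
| Major fall | Yes | Yes | Not applicable | No, unless counted as a fall-related fracture | Yes, no care condition |
| Road or water accident | Yes | Yes | Not applicable | Unclear: no care setting is named | Motor vehicle collisions only |

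**Capture of the death.** The second and third columns are complete. No death is lost to the trial.

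**Classification by harm.** For hemorrhagic stroke and heart failure, the cardiovascular-death definition does not help, because neither is among its causes. No outcome in 3.5.1 is hemorrhagic stroke or heart failure, so monitoring outcomes as safety events adds nothing by cause. Among the collection definitions, the 7.4.3 item is the only named by-cause category for these two harms, and it stops at hospitalization. The fatal-stroke case definition in 3.5.2 shows that the trial can classify such a death, but nothing in the text carries that classification into the 7.4.3 item.

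**Agreement between lists.** On its face, 8.1.3 includes fatal cases of hemorrhagic stroke and falls, since it sets no care condition. The definitions under which sites collect these events do not clearly do so. The two lists also differ on heart failure and on the scope of accidents.

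**Effect on the comparison of arms.** Let r1 and r0 be the true rates of a harm in the alcohol and abstention arms, and s1 and s0 the shares that are fatal out of hospital and so left out. The observed rate ratio is r1(1 − s1) / [r0(1 − s0)].

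- If s1 = s0 = s, the ratio is r1/r0, unchanged. The event count and the rate difference both shrink by the factor (1 − s).
- If s1 > s0, the ratio is pulled down; if s1 < s0, it is pushed up.

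The documents give no value for r1, r0, s1 or s0, so neither the number omitted nor the direction of any bias can be derived from them.

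**The case against.** The strongest defence has four parts.

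1. *The deaths are captured.* This stands in full. A reader might infer from 7.4.3 that such deaths go uncounted. The documents do not support that: they are SAEs, they reach the DSMB in listings, and they count in the primary endpoint. What is missing is the label by harm.

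2. *The care condition may be a severity threshold.* An event that requires hospitalization need not be one that received it, and a fatal stroke would pass a severity test. That reading is possible, but the text does not choose between the two, and sites could code the same death differently. For accidents the defence is strongest: no setting is named, so ambulance attendance at the scene could qualify. The accident item is therefore ambiguous and cannot be said to exclude scene deaths.

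3. *The list has another job.* Section 7.1 centres collection on SAEs and adds selected non-serious events, so the thresholds may only decide which lesser events to add. But 7.4.3 says that one of its events can also be an SAE, so its categories are not confined to non-serious events.

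4. *Definitions may sit elsewhere.* The Manual of Procedures is to hold standard event definitions, and the Safety Subcommittee is responsible for safety-outcome definitions and coding consistency. Either may already deal with fatal cases. This cannot be checked from the documents.

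Two further inferences are tempting. One is that the omission biases the comparison toward no harm. That needs alcohol to raise the share dying before care (s1 > s0), and the documents offer no evidence on it. The other is to put a number on the omission. Assumed hemorrhagic-stroke rates of 0.1–0.2% per year over 7,800 × 6 = 46,800 person-years give about 47–94 events, and an assumed 5–20% dying before admission gives about 2–19 omitted over both arms. The arithmetic is right, but both ranges come from outside the documents, so the result is not a finding about this trial.

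**Conclusion.** The point holds as a gap in cause-specific classification. On the literal wording, out-of-hospital deaths from hemorrhagic stroke, heart failure and major falls have no assured place in the named categories of 7.4.3, and for the first two the cardiovascular-death definition does not fill it. The by-arm counts can therefore miss fatal out-of-hospital cases of harms that the protocol itself associates with alcohol. The size is unknown, and any bias between arms is possible but not demonstrated.

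The conclusion assumes that the care condition is applied as written and that the Manual of Procedures does not already add fatal cases. It carries less weight for falls involving a fracture, which have their own item, and for accidents, where the wording is open. It is a worthwhile correction to definitions and does not call the capture of deaths into question.

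**What to change.** - In 7.4.3, define hemorrhagic stroke and heart failure as *fatal, or requiring hospitalization*, and major falls as *fatal, or requiring medical attention in hospital or an emergency ward*. State that road or water accidents include those fatal at the scene. Atrial fibrillation can stay as it is.
- Assign fatal cases to a category from the death certificates, coroner or autopsy findings and ambulance records listed in 7.3, using the fatal-stroke definition and subtype in 3.5.2 for hemorrhagic stroke.
- Reconcile 7.4.3 with 8.1.3 so that both use one set of events and definitions. The points to settle are the care condition, heart failure (absent from 8.1.3), and motor vehicle collisions against road or water accidents.
- Report fatal and non-fatal counts of each harm by arm to the DSMB.

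The cost is small: a change to the definitions, a field on the case report form, and a short coding rule. Deaths are already reported and the source records already provided for. The downside is some uncertainty of cause in unwitnessed deaths; the coding rule should say how these are classified, for example by marking the cause as probable and showing those cases separately.

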7.4.4 REPORTING OF PREGNANCY

The use of alcohol is a known risk factor during pregnancy. One of the main inclusion criteria in the trial is postmenopausal status. Therefore, women included in the trial will have a postmenopausal status and pregnancies are not expected to occur. However, if a pregnancy does occur, participation will be discontinued on the intervention.

7.4.5 INCIDENT CONDITIONS THAT RESULT IN PERMANENT OR TEMPORARY STOPPING OF ALCOHOL BUT CONTINUED FOLLOW-UP FOR OUTCOMES

The use of alcohol may be harmful in the following conditions. For this reason, the intervention will be discontinued at least temporarily in the following incident conditions (this list is not intended to be exhaustive):

- Dementia
- Heart failure Class III or IV
- Breast cancer
- Gastric bypass surgery
- Serious chronic liver disease (e.g., active hepatitis B and C infections) or liver tests (aspartate aminotransferase [AST], alanine aminotransferase [ALT] and gamma-glutamyl transpeptidase [GGT]) >2 times the upper limit of the normal range using local standards; GI bleeding.
- Estimated glomerular filtration rate (eGFR) drops to <30 ml/min /1.73m² or end-stage renal disease (ESRD)
- Ongoing use of any medication for which alcohol consumption is contraindicated
- A Patient Health Questionnaire (PHQ-9) score ≥15 or a positive response on question 9 dealing with suicide ideation
- Any organ transplant
- Pregnancy
- Development of alcohol use disorder

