6.2 LABORATORY PROCEDURES/EVALUATIONS

6.2.1 CLINICAL LABORATORY EVALUATIONS

Blood collection will occur at the screening visit, baseline visit, 3 months, 6 months and each annual visit. Specific laboratory assessments (e.g., liver function tests, serum creatinine) are important for determining eligibility status. During follow-up, laboratory results will be used to assess safety and for trial-related outcomes and markers of compliance. The amount of blood collected at one visit will be approximately 60 ml or about 4 tablespoons; part will be used for local safety labs, and the remainder will be stored either centrally or locally (local IRB/EC approval required) for other future biomarker analyses (see 6.2.1.2). Local sites may also collect and store additional blood with approval from the Ancillary Studies Committee, the MACH15 Steering Committee, and their IRB/EC.

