6.2.1.1 LOCAL LABORATORY ANALYSES

Laboratory analyses to be completed at the local laboratory include standard hematology and biochemistry tests: fasting glucose or hemoglobin A1c, aspartate aminotransferase (AST), alanine aminotransferase (ALT), gamma-glutamyl transferase (GGT), creatinine, total cholesterol, HDL-C, triglyceride, LDL-C. All local laboratories will be certified or controlled as per local rules or regulations.

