6.3.2 SCREENING

The in-person screening visit procedures include:

- Informed consent – Screening
- Contact information
- Medical history
- Concomitant medications
- Blood pressure and pulse
- AUDIT
- Y-BOCS-hd (3 items)
- Timeline Followback (7-day)
- PHQ-9
- Health Coaching (for adherence during washout)
- Blood draw for AST, ALT, GGT, and creatinine. Participants who have not had HDL, total cholesterol, in the prior 24 months will also need these at screening.
- A self-report physician diagnosis of diabetes is sufficient for the screening visit and for determining the cardiovascular risk score (lab value is not required). However, if the participant does not know, either fasting glucose or HbA1c (non-fasting) should be used (historical values within 24 months may be used).

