6.3.5 BASELINE/RANDOMIZATION

The baseline visit will be the randomization visit and will include the following assessments/procedures:

- Informed Consent – Randomization
- Anthropometrics, blood pressure, and pulse
- Concomitant medications
- Sociodemographics
- Blood draw for AST, ALT, GGT, and lipid panel (total cholesterol, HDL-C, triglycerides, and either measured or calculated LDL [if total cholesterol was drawn at screening, it does not need to be repeated]). Fasting glucose and/or HbA1c will be drawn per clinic preference. If the value is above the ADA-defined cutoff for pre-diabetes (see MOP for further detail), the participant will be asked to return to clinic for a second blood draw to confirm. (Participants with known diabetes need not have a second blood draw.)
- Collection of blood, urine and hair clippings (optional) for storage; optional genomic material will also be stored from this visit
- Smoking History
- Fagerstrom Test of Nicotine Dependence
- EQ-5D-5L™
- Confirmation of eligibility
- Behavioral assessment interview
- Randomization
- Coaching session on assigned intervention

Clinical sites may choose to do the baseline data collection and randomization over 2 visits. When the randomization is not done on the baseline visit day, the goal will be to do the randomization within 30 days. Continued eligibility will be confirmed on the day of randomization.

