6.3.6 FOLLOW-UP

After the baseline/randomization visit, participants will be seen in clinic for subsequent visits at 3 months, 6 months, 12 months, and then annually until close-out. Follow-up phone calls will occur at 2 weeks, 4 weeks, and 9 months during the first year, and every 3 months thereafter (except for annual

visits when participants are seen in clinic). See Table 6.1: Measures and Frequency for the sequence of events and special considerations (e.g., fasting visits) and the MOP regarding visit windows.

6.3.6.1 3 AND 6 MONTH IN-PERSON VISITS

- Contact information updated
- Blood pressure and pulse
- Blood draw for AST, ALT, GGT, HDL-C
- Timeline Followback (7-day)
- YBOCS-hd (3 items)
- Health Coaching (for adherence)
- Assessment for SAEs and MACH15 AEs
- Assessment for CVD outcomes

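### Alcohol is to stop if eGFR falls below 30, but creatinine is scheduled only at screening, so no scheduled follow-up test would find an undiagnosed fall

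*Combined protocol and SAP*

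**What the plan says.** Section 7.4.5 states that alcohol may be harmful in certain conditions and that "the intervention will be discontinued at least temporarily in the following incident conditions". The list includes "Estimated glomerular filtration rate (eGFR) drops to <30 ml/min /1.73m² or end-stage renal disease (ESRD"). The same limit is an entry exclusion (section 4.3, item 14), so a participant may enter with an eGFR of 30 or just above.

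The screening visit (6.3.2) specifies "Blood draw for AST, ALT, GGT, and creatinine", and Table 6.1 marks the Creatinine row in the screening column alone. Later draws leave it out: baseline is "Blood draw for AST, ALT, GGT, and lipid panel" plus glucose or HbA1c (6.3.5), and months 3 and 6 are "Blood draw for AST, ALT, GGT, HDL-C" (6.3.6.1). The annual draw covers liver tests, HDL-C and, for diabetes, glucose or HbA1c (6.3.6.2). Early termination repeats the annual assessments (6.3.7).

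Section 6.2.1 describes the purpose of the tests in two sentences: "Specific laboratory assessments (e.g., liver function tests, serum creatinine) are important for determining eligibility status", and "During follow-up, laboratory results will be used to assess safety". Section 6.2.1.1 begins "Laboratory analyses to be completed at the local laboratory include standard hematology and biochemistry tests" and names creatinine among them, without assigning it to a visit.

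**The concern.** A stopping limit expressed as a laboratory value can be applied only if someone measures that value. Here the trial measures it once, before randomization, and the limit applies for years afterwards. With the plan followed as written, a participant whose eGFR has fallen below 30 without being diagnosed can remain assigned to daily alcohol, in a condition where the protocol itself says alcohol may be harmful.

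The basis is the protocol's own rule. Section 1.4.1 lists no renal harm from alcohol, and none is asserted here. What is at stake is whether a safety rule the investigators chose to write can work during follow-up.

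**Working it through.** The plan gives no figure to reproduce; the check compares the rule with the schedule.

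**Step 1. Where the relevant tests are scheduled.**

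| Contact | Source | Liver tests | Creatinine |
|---|---|---|---|
| Screening | Table 6.1, 6.3.2 | yes | yes |
| Baseline | Table 6.1, 6.3.5 | yes | no |
| Months 3 and 6 | Table 6.1, 6.3.6.1 | yes | no |
| Annual | Table 6.1, 6.3.6.2 | yes | no |
| Close-out, early termination | Table 6.1, 6.3.7 | yes | no |
| Phone calls | 6.3.6.3, 6.3.6.4 | no blood draw | no blood draw |

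Three other passages might seem to supply the test. The list in 6.2.1.1 has no timing. Section 7.1 mentions laboratory tests at follow-up, but its example is liver function. Appendix B lists creatinine only as a potential assay on stored samples. None schedules a creatinine after screening.

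**Step 2. Comparison with the other cut-offs in 7.4.5.** Liver tests above twice the upper limit of normal are checked at every follow-up clinic visit. PHQ-9 of 15 or more is checked at every annual visit (6.1.1.3). eGFR below 30 is the only laboratory or questionnaire cut-off in the list with no scheduled follow-up measurement.

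**Step 3. Draws between randomization and close-out.** Close-out is left out because the intervention ends then.

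- 4.5 years: months 3, 6, 12, 24, 36, 48 = 6 draws, of which 4 are annual.
- 6 years exactly: months 3, 6, 12, 24, 36, 48, 60 = 7 draws, of which 5 are annual.
- 7.5 years: the same plus months 72 and 84 = 9 draws, of which 7 are annual.

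Creatinine is in 0 of them at every follow-up length.

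**Step 4. Average number of annual draws.** Follow-up runs from 4.5 to 7.5 years (3.1, 11.4). Assume accrual is uniform over the 3 years. Then follow-up is 4.5–5 years for a share 0.5/3 (4 annual draws), 5–6 years for 1/3 (5 draws), 6–7 years for 1/3 (6 draws) and 7–7.5 years for 0.5/3 (7 draws):

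(0.5×4 + 1×5 + 1×6 + 0.5×7) / 3 = 16.5 / 3 = 5.5 per participant.

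For 7,800 participants: 7,800 × 5.5 = 42,900 assays before losses (21,450 per arm).

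**Step 5. Allowing for the plan's 1% annual loss (8.2).** The probability that follow-up extends beyond year k is 1 for k = 1 to 4, 2.5/3 for k = 5, 1.5/3 for k = 6 and 0.5/3 for k = 7. Expected assays per participant:

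0.99 + 0.99² + 0.99³ + 0.99⁴ + (2.5/3)×0.99⁵ + (1.5/3)×0.99⁶ + (0.5/3)×0.99⁷ = 3.901 + 0.792 + 0.471 + 0.155 = 5.32.

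7,800 × 5.32 ≈ 41,500.

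**Step 6. What cannot be computed.** The number of missed cases would need the incidence of eGFR below 30 in this population and the share already found in outside care. The documents give neither, so no estimate is made.

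**The case against.** The strongest reply is that 7.4.5 tells sites what to do once a condition is known and promises no surveillance. Dementia, breast cancer and class III or IV heart failure have no scheduled diagnostic test either. Liver tests have reasons of their own: liver damage is a listed risk (1.4.1), and raised values are reportable (7.4.3) and monitored (8.1.3). Renal function appears in none of those places. Testing for expected effects of alcohol and leaving the rest to clinical care is a coherent policy.

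Part of this stands. The rule and the schedule do not contradict each other, and unscheduled clinical diagnoses are normal in such a list. But dementia and breast cancer usually come to attention as diagnoses, whereas an eGFR value exists only if creatinine is measured. Reading 7.4.5 as act-on-knowledge leaves that knowledge to chance contact with outside care.

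A reader might go further and infer that the eGFR rule can never be triggered. The documents do not support that. Medical events and symptoms are solicited at each visit and medications reviewed annually (6.1.1.4). The serious adverse event definition is not confined to hospitalization (7.1.2), and medical records and spontaneous reports are further routes (7.3). Section 1.3.3 expects this population to have more health-care contact than most. End-stage disease would normally be known clinically. These routes narrow the gap to a fall that nobody has diagnosed, but do not close it.

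Procedural detail is also deferred to the Manual of Procedures, which may add a test. That limits what can be said about practice at the sites, but not about the schedule in the protocol.

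**Conclusion.** The point holds in its limited form. The protocol has a numeric stopping limit for alcohol and schedules no measurement after screening that could show it has been crossed: 0 of 6 to 9 draws, depending on length of follow-up. The omission itself is certain from the text. Its clinical consequence is of unknown size, because neither the incidence of eGFR below 30 nor its detection elsewhere is given.

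A reader might also infer that the primary comparison is affected or that alcohol damages the kidney. Nothing in the documents supports either, and the concern is confined to participant safety. It merits correction because the remedy is cheap and uses blood already drawn.

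**What to change.** Add creatinine with calculated eGFR to the existing annual local safety draw, in both arms and on the same schedule.

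- **Table 6.1:** mark the Creatinine row in the column for 12 months and every 12 months after. Add a footnote that it is not required at close-out or early termination; the footnote is needed because 6.3.7 equates those assessments with the annual visit.
- **Section 6.3.6.2:** add creatinine with calculated eGFR to the annual draw.
- **Section 7.4.5:** add, for example, *The eGFR criterion is checked at each annual visit, acted on whenever a value below 30 becomes known from any source, and rechecked before alcohol is restarted after a temporary stop.*

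Testing the alcohol arm alone would halve the assays, since only that arm has alcohol to stop, but it is the worse choice. Outcomes are to be assessed in the same way and on the same schedule in both groups (6.1.1.4). Renal results in one arm could prompt extra medical contact there, and the primary endpoint includes angina admissions and revascularization. A trial creatinine seen in only one arm could also reveal assignment to the masked site reviewers (3.5, 7.2.1).

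The cost is a protocol amendment, site review of results, and one routine assay per annual visit: about 42,900 in both arms before losses, or about 41,500 with 1% annual loss. No visit or venepuncture is added. Annual testing still leaves the first 12 months unchecked; if participants entering just above 30 are a worry, the draws at months 3 and 6 could carry the assay too, at 7,800 × 2 = 15,600 more before losses.
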